1 ABSTRACT

1.1 Type of study

Prospective, multicenter, comparative, open-label, randomized and controlled pilot study

1.3 Title

Pilot study fatty liver and obesity: MR fat quantification and MR elastography during a very low-calorie-ketogenic diet (Pronokal Method®) versus a low calorie diet

1.4 Protocol Code

PNK-FATLIV-2016-04

1.8 Study design

Prospective, multicenter, open-label, randomized and controlled study of the effects of weight loss and reduced visceral fat on non-alcoholic fat infiltration into liver after a very low calorie ketogenic diet (VLCK diet) (Pronokal® Method) versus a hypocaloric diet, with a 6-month follow-up.

1.9 Study objectives

- To evaluate the effects of body weight loss after a very low-calorie-ketogenic diet (Pronokal Method®) versus low calorie diet, on visceral fat reduction, liver fatty infiltration, using a new MRI technique of fat liver quantification (Ideal IQ**).
- To correlate the degree of liver fat infiltration and liver stiffness using MR Elastography
- To investigate the hypothesis of a linear correlation between adrenal gland size and variables commonly associated to insulin resistance such as BMI, visceral fat and liver steatosis.

1.10 Condition in study

Fat infiltration into the liver (nonalcoholic fatty liver disease)

1.11 Study treatment

A very low-calorie-ketogenic diet (Pronokal Method®)

1.12 Outcome Measures

- Body weight loss
- Visceral fat (measured by the area in squared centimeters at the level of the 3rd vertebrae, using MRI technique)
- Porcentaje de contenido graso del hígado
- Liver stiffness using MR Elastography
- Linear measurements of the adrenal glands
- Salivary cortisol levels

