7 SUBJECT SELECTION

7.1 Study population

Obese patients of either sex with BMI over 30 kg/m², who agree to participate in the study.

7.2 Inclusion criteria:

- Patients of either sex, older than 18 years
-

-
- Obese patients with BMI equal or over 30kg/m²
 - Patients who agree to participate and sign the Informed Consent

7.3 Exclusion criteria:

- Pregnant or lactating women.
 - Patients weighing over 140 kg (by limitation of the MRI device)
 - Patients on anti-obesity drugs (eg, sibutramine, orlistat and liraglutide) or weight-interfering medications (eg, topiramate). In such cases a wash out period of 3 months is required.
 - Patients with alcohol intake > 20 g/day in women and > 30 g/day in men.
 - Patients with liver failure or with pathologies that may affect the liver
 - Patients with other causes of liver steatosis: chronic viral hepatitis and/or drug intake (corticosteroids, estrogens, NSAIDs, calcium antagonists, amiodarone, tamoxifen, tetracyclines, chloroquine, antiretrovirals, perhexiline).
 - Patients with eating disorders.
 - Patients with any psychiatric disorder (eg schizophrenia, bipolar disorder, substance abuse, severe depression).
 - Patients receiving dicumarinic anticoagulants (Sintrom®).
 - Patients taking corticosteroids.
 - Patients with severe kidney failure (gfr <30).
 - Patients with type 1 and type 2 diabetes mellitus.
 - Patients with hemopathies, including coagulation disorders
 - Patients with cardiovascular or cerebrovascular disease (of heart rate disorders, recent infarction [$<6m$], unstable angina, decompensated heart failure, recent stroke [$<6m$]).
 - Patients in acute attack of gout.
 - Patients with renal lithiasis verified by ultrasound.
 - Patients with cholelithiasis verified by ultrasound.
 - Patients with electrolyte imbalance, according to medical criteria.
 - Patients with orthostatic hypotension.
 - Patients with cancer or history of cancer who have not been discharged from oncology
 - Patients who are not expected to attend follow-up visits
-

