9 STUDY PROCEDURES AND OUTCOME MEASURES

9.1 Outcome measures

9.1.1 *Primary variables*

- Liver fatty infiltration, measured by a MRI technique of fat liver quantification (Ideal IQ**).
- Visceral fat, measured by the area in squared centimeters at the level of the 3rd vertebrae, using MRI technique.

9.1.2 *Secondary variable*

- Liver stiffness detected by MR Elastography
- Adrenal gland linear measurement
- Body weight
- Salivary cortisol levels

9.1.3 *End points*

- Reduction of fat infiltration into the liver between the baseline visit and 2 months (or end of the ketosis stage) and between the baseline visit and the control visit at month 6 of treatment.
- Visceral fat reduction between the baseline visit and 2 months (or end of the ketosis stage) and between the baseline visit and the control visit at month 6 of treatment.
- Correlation between degree of liver fat infiltration and liver stiffness
- Correlation between adrenal gland size and BMI, visceral fat and liver steatosis.
- Correlation between salivary cortisol levels and BMI, visceral fat and liver steatosis.
- Weight loss between the baseline visit and 2 months (or end of the ketosis stage) and between the baseline visit and the control visit at month 6 of treatment.

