10.2 Analysis of objectives

For the analysis of the primary objective and the secondary objectives, the differences between visits and between groups will be studied for the changes in the ratio between liver fat and the degree of steatosis (measured by MRI), changes in the degree of liver stiffness, changes in cortisol levels in saliva, weight changes, BMI and waist circumference, and changes in the amount of visceral fat among visits. The qualitative variables will be compared using Fisher's exact test, and the quantitative variables will be compared by means of the Student's t test for paired data. If the conditions to apply the Student's t test are not met, we will use the non-parametric Mann-Whitney U test. In the case of comparing paired data, we will use the tests described above, in their version for comparing this type of data.

The Pearson correlation coefficient or Spearman's correlation coefficient if the application conditions are not met will be used to study the following: the association between reduction of hepatic steatosis and weight loss and loss of visceral fat; the association between hepatic steatosis and liver stiffness; and the association between adrenal gland size and salivary cortisol levels with weight changes, BMI, hepatic steatosis and visceral fat.

For all tests, the significance level will be set at $p < 0.05$.

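### Section 10.2 compares changes in percent liver fat, a primary variable bounded at zero, without baseline adjustment or a stated scale; if the diets act proportionally, power is lost

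*Combined protocol and SAP*

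**What the plan says.** - **Unit and status.** Section 1.12 lists the outcome, in Spanish, as "Porcentaje de contenido graso del hígado". Section 9.1.1 makes it one of two primary variables: "Liver fatty infiltration, measured by a MRI technique of fat liver quantification".
- **Endpoint.** Section 9.1.3 gives "Reduction of fat infiltration into the liver between the baseline visit and 2 months (or end of the ketosis stage", and likewise from baseline to month 6. It does not say whether the reduction is absolute or relative.
- **Quantity analysed.** Section 10.2 speaks of "changes in the ratio between liver fat and the degree of steatosis (measured by MRI". That ratio is not defined anywhere. No log, percent-change or ratio-to-baseline scale is named.
- **Test.** "the quantitative variables will be compared by means of the Student's t test for paired data"; if its conditions fail, "we will use the non-parametric Mann-Whitney U test". There is no baseline covariate. Because Section 10.2 then refers paired data to the paired versions of its tests, I take the between-arm test to be the two-sample t test.
- **Entry.** Section 7.2 admits "Obese patients with BMI equal or over 30kg/m²" and sets no minimum liver fat. The liver blood tests in Section 9.2.1 only flag suspected steatosis; they are not an inclusion criterion.
- **Size.** Sections 7.4 and 7.5 give 20 per group for an exploratory pilot, without effect size, SD or power.

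**The concern.** With entry by BMI alone, starting liver fat may run from near normal to high. A patient at 3% cannot lose 5 points; a patient at 25% can. If each diet removes a fraction of the fat, both the change in points and its spread grow with the starting value. An unadjusted comparison of point changes then gives most weight to high starters and carries the baseline spread as noise, so it may miss a real difference. Entering raw baseline as a covariate helps, but does not remove variance that grows with baseline. The Section 10.2 correlations of steatosis reduction with weight loss and visceral fat loss inherit the same dependence on starting fat.

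The unstated scale is a weakness in itself. In an open-label trial it leaves the form of a primary comparison to be settled once data exist.

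**Working it through.** **1. The plan's own figure.** The 20 per group cannot be reproduced, since no effect size, SD or power is given. For context, at two-sided 0.05 (sidedness assumed) and 80% power the detectable standardised difference is (1.960 + 0.842) × √(2/20) = 0.89. Power at a standardised difference of 0.8 is 0.72.

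**2. What a proportional effect does on each scale.** Assume falls of 50% and 25%. A patient starting at 3% falls by 1.5 or 0.75 points, an arm difference of 0.75. A patient starting at 25% falls by 12.5 or 6.25 points, an arm difference of 6.25. The ratio of follow-up values is 0.50/0.75 = 0.67 for both.

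**3. Concentration of the signal.** Under step 2 the arm difference in points is proportional to baseline, so the top quarter's share of it equals its share of baseline fat. For a lognormal baseline with log SD σ that share is Φ(σ − 0.674), against 0.25 if spread evenly:

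- σ = 0.4: Φ(−0.274) = 0.39
- σ = 0.7: Φ(0.026) = 0.51
- σ = 0.9: Φ(0.226) = 0.59

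In simulated samples of 40 the shares are 0.39, about 0.50 and 0.57. With median 6% and σ = 0.9, the fraction starting below 5% is Φ(ln(5/6)/0.9) = 0.42.

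**4. Power by simulation, 20 per arm.** No input comes from the documents; all are assumptions. Set A: lognormal baseline with median 5-12% and log SD 0.6-0.9, falls of 50% v 25%, patient-level log SD 0.4, measurement error 0.3-0.8 points.

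| Set A setting | t test, change in points | Mann-Whitney, change in points | ANCOVA, raw | ANCOVA, log |
|---|---|---|---|---|
| Median 8%, log SD 0.9, error 0.3 | 0.38 | 0.51 | 0.62 | 0.83 |
| Median 12%, log SD 0.6, error 0.3 | 0.57 | 0.63 | 0.72 | 0.86 |
| Median 8%, log SD 0.9, error 0.8 | 0.37 | 0.44 | 0.58 | 0.63 |
| Median 5%, log SD 0.6, error 0.8 | 0.47 | 0.47 | 0.61 | 0.58 |

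Across set A: about 0.34-0.63 for the two planned tests, 0.53-0.73 for raw ANCOVA and 0.50-0.86 for log ANCOVA.

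Set B varied the assumptions: median 6-12%, log SD 0.4-0.9, falls of 40 v 25, 50 v 25 or 60 v 30%, residual log SD 0.3 or 0.5, error 0 or 0.7 points (0.5 added before taking logs when error is present). Without error, log ANCOVA matched or beat raw ANCOVA in all 24 settings, by 0 to 26 percentage points of power. With error the gain shrank, and log was 0 to 4 points worse in 6 of 24 settings, all with median 6% and residual log SD 0.3. In the setting with median 6%, log SD 0.9, 50 v 25% and residual 0.5, the four powers were 0.33, 0.43, 0.44 and 0.70 without error, and 0.33, 0.38, 0.42 and 0.50 with it.

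**5. Type I error.** With no arm difference, rejection was 0.043-0.050 for all four tests.

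**6. Constant-point effect.** Baseline 15% (SD 4), falls of 3 v 5.5 points, residual SD 3: t test 0.72, Mann-Whitney 0.70, raw ANCOVA 0.71, log ANCOVA 0.54. In a wider set of constant-point settings, log ANCOVA had 0.34-0.66 and raw ANCOVA 0.51-0.83.

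**7. Near-zero readings.** In set A at log SD 0.9 and error 0.8, at least one reading was zero or negative in about 85% of trials at median 5% and 53% at median 8%. At median 5% raw ANCOVA had 0.53; log ANCOVA had 0.53 with readings floored at 0.5 but 0.43 with a floor of 0.1, below the range in step 4. At log SD 0.6 the three figures were 0.62, 0.59 and 0.52.

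**The case against.** - **The documents do not say raw points.** A reader might infer that the plan chose the percentage-point scale. It did not: Section 9.1.3 says only reduction, and the ratio in Section 10.2 is undefined. This stands. The defect is an unspecified scale, with points as the natural reading.
- **The simulations favour their own model.** Data generated with proportional effects will usually favour a log analysis, and nothing in the documents shows that the diets act proportionally. Step 6 reverses the ranking. This stands, and is why the point difference must be kept.
- **Much of the gain is baseline adjustment, not scale.** Also true. At the ends of the set A ranges, adjustment takes 0.34-0.63 to 0.53-0.73, and the log scale changes that to 0.50-0.86. Adjustment is the safer part of the fix: it cost at most about 0.01 of power in any setting run.
- **The plan already has rank-based fallbacks.** Mann-Whitney recovers part of the loss (0.38 to 0.51 in the first table row), and Spearman is available for the correlations. Ranks limit extreme values but do not remove dependence on starting fat.
- **It is a pilot, and the test is valid.** No power is promised, type I error holds, and a mean point difference is a legitimate randomised comparison that does not require a constant effect. This limits the severity. Section 10.2 nevertheless tests at 0.05 with 40 patients, so efficiency and an interpretable estimate matter.

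**Conclusion.** The point holds in a conditional form. For a primary variable with a floor at zero and no liver-fat entry level, Section 10.2 fixes neither the scale of change nor any baseline adjustment. If change means points and the diets act roughly proportionally on a skewed baseline, the planned tests have power of about 0.34-0.63, where baseline-adjusted analyses reach 0.53-0.73 (raw) or 0.50-0.86 (log). These figures rest entirely on assumed inputs.

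Three stronger readings are not supported:

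- **That the result hangs on a few patients.** The top quarter carries about 40-57% of the signal, which is disproportionate but far from all of it.
- **That the log scale is always better.** It can fall slightly below raw ANCOVA when fat is low and measurement error is large, and falls clearly below it under a constant-point effect.
- **That the comparison is biased.** False-positive rates are at their nominal level; this is a matter of power and interpretation.

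**What to change.** In Section 10.2:

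1. Compare arms on liver fat at months 2 and 6 by ANCOVA with baseline liver fat as covariate.
2. Pre-specify the relative scale: log liver fat on log baseline, with the arm effect reported as a ratio with 95% CI. Replace or define the ratio now named there.
3. State a fixed rule for zero, negative or near-zero readings, such as a named floor or offset, with a sensitivity check on its value.
4. Report the baseline-adjusted percentage-point difference alongside, as a supporting analysis.
5. Use the relative reduction in the correlations with weight loss and visceral fat loss.

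The cost is wording only: no new visits, scans or patients. The downside is that the log scale is noisier near zero, depends somewhat on the chosen floor, and loses power if the true effect is a constant number of points. Item 4 covers that case and should not be dropped.

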1.13 Study population and number of subjects

Obese patients of either sex with a BMI over 30 kg/m².

1.14 Follow-up and duration of the study

The follow-up will be 6 months.

1.15 Funding

We were awarded a grant from PronoKal Group® to partially fund this study, where MR image acquisition and post-processing costs will be covered. The leading investigators, free of charge, will do all data analysis and manuscript writing.

1.16 Schedule

Study onset: May, 2016.

Completion of study: May, 2017.

3 GENERAL INFORMATION

3.1 Title

Fatty Liver and obesity: MR Fat Quantification and MR Elastography during a very low-calorie-ketogenic diet (Pronokal Method®) versus a low calorie diet. A multicenter randomized controlled clinical trial.

3.2 Protocol code

PNK-FATLIV-2016-04

3.3 Type of study

Prospective, multicenter, open-label, randomized and controlled study of the effects of weight loss and reduced visceral fat on non-alcoholic fat infiltration into liver after a very low calorie ketogenic diet (VLCK diet) (Pronokal® Method) versus a hypocaloric diet, with a 6-month follow-up.

3.4 Study treatment

A very low-calorie-ketogenic diet (Pronokal Method®)

3.7 Expected duration

The expected duration of the study is 10 months (4 months of recruitment and 6 follow-up months).

4 INTRODUCTION AND RATIONALE OF THE STUDY

The liver histology in obese people can be altered by an accumulation of intrahepatic triglyceride (IHTG), i.e., steatosis, which is the hallmark feature of nonalcoholic fatty liver disease (NAFLD). Nonalcoholic fatty liver disease (NAFLD) is the liver manifestation of the complex metabolic derangements associated with obesity, being an emerging epidemic in Western countries and affects all ages and ethnicities. Individuals with hepatic steatosis alone were thought to have a benign long-term prognosis. However, up to 25% of these patients may develop nonalcoholic steatohepatitis (NASH), which may progress to cirrhosis in susceptible individual (5). Because early NAFLD may be reversible, screening and early intervention may be indicated (1-2).

Weight loss alone by dietary changes has been shown to lead to histological improvement in fatty liver making nutrition therapy to become a cornerstone of treatment for NAFLD. Studies show that those who achieved a minimum of 7% weight loss had improvements in their liver histology (3). In recent years the VLCD diets, especially in combination with intensive life interventions (ILI), are gaining recognition as a suitable alternative to conventional low-calorie diets for weight loss (6-8), with greater weight loss at short and long term (9-11). PronoKal® method is a commercially available weight loss program, which includes a dietary regime (very low-calorie-ketogenic diet based on a high-biological-value protein preparations diet and natural foods followed by low calorie diet), lifestyle and behavioral modification support. This method has proved more effective for weight loss compared with a standard low-calorie diet, achieving a reduction of more than 10 % of the initial weight at 2 months in 96 % of the patients, and in 100% of the patients at 4 months (11).

Liver biopsy is the gold standard in diagnosing NAFLD and the most accurate tool for grading fibrosis. However, is invasive and carries the risk of complications (3). Also, histological examination of biopsy samples is subject to sampling error due to histological heterogeneity. Scoring is semi-quantitative, limiting its ability to detect modest changes, and scoring results vary between reports precluding direct comparisons. Various imaging techniques are proposed for liver fat quantification. Liver fat fraction (FF) can be calculated using fat and water MRI signal intensities in chemical-shift images (in-phase [IP] and out of phase [OP] sequences). Typically, the fatty liver shows increase in signal intensity (SI) on IP images and shows diffuse signal drop in OP image. The fat fraction can then be determined by calculating the loss of SI in OP images as compared to IP images. From congruent sets of IP and OP images,

acquired within the same breath-hold sequence, the fat fraction can be calculated pixel-wise, and misregistration errors can be avoided (4). MRI multiecho method estimates T2* from six different echo times (TE). This method resulted in improved diagnostic specificity compared with that of the triple-echo method which caused systematic underestimation at high FFs (1). New noninvasive methods including MR elastography have been developed for o distinguish necroinflammation and mild fibrosis from simple steatosis (4). Given that the spectrum of fatty liver disease ranges from simple steatosis, through stages of liver cell injury (steatohepatitis), to fibrosis, and eventually to cirrhosis, it is appropriate to ask whether hepatic stiffness as a biomarker can be used to identify the presence of liver cell injury prior to the onset of fibrosis.

One of the leading extra-hepatic causes of liver steatosis is metabolic syndrome (MS). Although, multiple definitions of MS exists; the essential components of MS include insulin resistance, increased levels of stress hormones, such as cortisol, and visceral obesity. In the obese population, the hallmarks of a metabolic syndrome are highly prevalent, being peripheral insulin resistance and increase levels of stress hormones the leading causes of organ injury. In such individuals higher levels of cortisol are expected, secondary to an over activated hypothalamic-pituitary-adrenal (HPA) (13, 14). A linear correlation between adrenal gland volume and metabolic syndrome has been demonstrated, with increased adrenal volume in patients under a metabolic syndrome status. However, once these patients are engaged on a treatment regime, leading to weight loss and diminished insulin resistance, the increase in adrenal volume tends to be reversible. Adrenal volume measurements can be achieved using cross-sectional imaging and semi-automated softwares. In clinical practice, adrenal gland dimensions are generally assessed using limb linear measurements on multidetector row computed tomography or magnetic resonance imaging (15,16).

We conducted a prospective longitudinal clinical study to correlate the effects of a very low-calorie-ketogenic diet (PRONOKAL method*), body weight loss and visceral fat reduction, with liver fat fraction, using a new MRI model of fat liver quantification (Ideal IQ**). Additionally, the degree of liver fat and its evolution, during the diet program, will be correlated with liver stiffness using MR Elastography. Adrenal gland measurements will also be made using the linear technique described by Carsin-Vu A. (16) to address its correlation with weight loss, visceral fat and liver steatosis.

5 STUDY OBJECTIVES

5.1 Primary aim

- To evaluate the effects of body weight loss after a very low-calorie-ketogenic diet (Pronokal Method®) versus low calorie diet, on visceral fat reduction, liver fatty infiltration, using a new MRI technique of fat liver quantification (Ideal IQ**).

5.2 Secondary aims

- To correlate the degree of liver fat infiltration and liver stiffness using MR Elastography
- To investigate the hypothesis of a linear correlation between adrenal gland size and variables commonly associated to insulin resistance such as BMI, visceral fat and liver steatosis.

6 STUDY DESIGN

6.1 Type of study

Prospective, multicenter, comparative, open-label, randomized and controlled pilot study

6.2 Randomization process

Patients will be randomized at the time of inclusion, in accordance with an automatically generated randomization list. One group will start treatment with a very low calorie and ketogenic diet (VLCK diet group) while the other group will start a low calorie diet (control group). The patient ratio in both groups will be 1: 1.

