7.4 Number of subjects

A total of 40 patients will be included: 20 patients randomly assigned to a very low-calorie-ketogenic diet (VLCK diet group) and 20 patients randomly assigned to low calorie diet (control group).

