13 PRACTICAL CONSIDERATIONS

13.1 Workplan

The investigators will be in charge of recruiting patients. Once the patients have confirmed their willingness to participate in the study, the investigator should verify if they meet the inclusion/exclusion criteria of this study. If they are eligible, they will be requested the additional tests (blood test with liver function) and will be informed on every issue of the study through the Patient Information Sheet (Attachment 1).

At the baseline visit, once the complementary tests have been reviewed and verified to meet inclusion criteria, the physician must confirm that the patient agrees to participate in the study and obtain the patient's signature of the Informed Consent (Attachment 2). Upon signing, the investigator will verify the assigned group according to the randomization list.

At this baseline visit, the physician should request MRI and MR Elastography to assess the degree of hepatic steatosis, the amount of visceral fat and liver stiffness. The physician will also perform the first salivary cortisol test on the patient. Also, he should record the clinical data requested in the Data Collection Notebook and schedule the treatment.

During the weight loss treatment, patients in the study group will be monitored by the investigator fortnightly during the protein diet (Ketogenic Active Stage), although at these additional visits no data are expected to be collected for the study. Upon completion of the first two months of follow-up, the study group will end the ketogenic stage and from that moment on, the patients will be controlled outside the center by dietitians specialized in the Pronokal® Method. Patients in the control group (hypocaloric diet) will undergo controls at the center monthly, although data will only be recorded in the visits arranged in this protocol (screening, baseline, month2 and month 6).

At the moment the patient completes the two months of follow-up, the data requested in the DCN will be recorded, the salivary cortisol test will be performed and an MRI and a MR Elastography will be requested.

The investigator, apart from monthly visits or any additional visits deemed necessary, will have an appointment with the patient at month 6 of treatment for a new clinical assessment, will record the anthropometric data, and request a Control MRI and MR Elastography.

At the end of the 6-month follow-up, the study will be completed.

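### Section 6.2 describes no stratification or blocking for a 40-patient multicentre trial and 10.2 adjusts for nothing, so chance imbalance by centre or sex is neither limited nor accounted for

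*Combined protocol and SAP*

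**What the plan says.** Section 6.1 gives the design as "Prospective, multicenter, comparative, open-label, randomized and controlled pilot study". Section 7.4 sets the size at 40, with 20 per arm, and section 7.2 admits "Patients of either sex, older than 18 years", with no quota or expected split by sex.

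On allocation, section 6.2 states: "Patients will be randomized at the time of inclusion, in accordance with an automatically generated randomization list". It adds "The patient ratio in both groups will be 1: 1". The workplan in 13.1 describes the list in use: "Upon signing, the investigator will verify the assigned group according to the randomization list". No section mentions strata, blocks, minimisation or separate lists by centre.

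On analysis, section 10.2 says that "the quantitative variables will be compared by means of the Student's t test for paired data" and continues: "If the conditions to apply the Student's t test are not met, we will use the non-parametric Mann-Whitney U test". The first is a test for paired data and the second compares independent groups, so the exact between-arm test is not clear. On either reading it contains no centre, sex or baseline term. No adjusted or sensitivity analysis is planned.

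**The concern.** In a large trial an overall list balances most factors well enough. With 40 patients it often does not. Two factors deserve attention.

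- **Centre.** Patients are seen and counselled at the centre, both diets come with physical exercise, and nobody is masked. Delivery may therefore differ between centres.
- **Sex.** Visceral fat area is a primary variable, and it is reasonable to allow for a difference between men and women.

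If either factor falls unevenly across the arms, part of the observed difference in that one trial reflects the factor rather than the diet. The unadjusted test cannot separate the two. Even with balanced arms, it leaves variation due to centre, sex and baseline value in the error term. A baseline table with visibly uneven arms would also make the results harder to defend.

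**Working it through.** **Inputs.** From the plan: 40 patients, 20 per arm (7.4); 1:1 ratio (6.2); both sexes eligible (7.2). Assumed: the list ends at exactly 20:20; the number of men is 20 or 12; the centres are equal in size. The plan gives no sex split, and the study locations (1.7) are not readable in the copy reviewed. The plan states no figure on balance, so there is none to reproduce.

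**Imbalance by sex.** With a list fixed at 20:20 and 20 men, the number of men k in the ketogenic arm is hypergeometric:

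P(k) = C(20,k) × C(20,20−k) / C(40,20), with C(40,20) = 137,846,528,820.

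- k = 10: 184,756² / C(40,20) = 0.248
- k = 9 or 11: 2 × 167,960² / C(40,20) = 0.409
- k = 8 or 12: 2 × 125,970² / C(40,20) = 0.230
- k = 7 or 13: 2 × 77,520² / C(40,20) = 0.087

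A gap of 4 or more men: 1 − 0.248 − 0.409 = 0.343, or 34%. A gap of 6 or more: 0.343 − 0.230 = 0.113, or 11%. With 12 men the same calculation gives 30% and 8%.

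**Imbalance by centre.** Two centres of 20 follow the same distribution, and one centre's split mirrors the other's. So 12:8 or worse has probability 34%, and 14:6 or worse has 0.113 − 0.087 = 0.026, about 3%. The chance that at least one centre splits 70:30 or worse depends strongly on the number of centres (100,000 simulated permutations for each):

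| Equal centres (assumed) | At least one centre 70:30 or worse |
|---|---|
| 2 | 3% |
| 3 | 15% |
| 4 | 64% |

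Part of the jump from three to four is discreteness: in a centre of 10 the threshold is met at 7:3, while in centres of 13 or 14 it takes 10:3 or 10:4.

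**If the list is simple randomisation.** Blocking is not stated, so this is possible. An exact 20:20 split then has probability 12.5%, and the arms differ by 6 or more patients with probability 43%. Among 20 men, a gap of 4 or more has probability 50%.

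**Effect on the result.** A gap of 4 men is 4/20 = 20 percentage points. If men and women differ by 0.5 to 1.0 SD in the outcome (assumed), the unadjusted difference shifts by 0.20 × 0.5 = 0.10 SD to 0.20 × 1.0 = 0.20 SD. The standard error at 20 per arm is √(2/20) = 0.32 SD. The shift is thus about one third to two thirds of a standard error.

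**After the change.** With permuted blocks of 4 and 6 within centre, the gap inside a centre comes only from its last, incomplete block and cannot exceed 3. A 12:8 split (a gap of 4) can no longer occur in a centre.

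**Cost in degrees of freedom.** The two-group test has 40 − 2 = 38. ANCOVA with intercept, arm, baseline, sex and C − 1 centre terms has 40 − 4 − (C − 1): 35 with two centres, 33 with four.

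**The case against.** Several stronger readings are tempting, and the documents do not support them.

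- **That the list is known to be unstratified.** Sections 6.2 and 13.1 do not describe its structure. A blocked or stratified list could exist unreported. What can be said is that none is described.
- **That imbalance biases the trial.** Chance imbalance under randomisation leaves the estimator unbiased on average and the test valid. The assumed sex shift of 0.10 to 0.20 SD lies inside one standard error.
- **That centres differ in scanners or delivery.** Neither the number of centres nor the number of scanners can be seen. The weight limit in 7.3 refers to a single MRI device, 12.2 names one ethics committee, and 13.1 moves ketogenic-diet patients to specialised dietitians outside the centre after month 2. The 64% figure needs four equal centres; with two, a 70:30 split is rare.
- **That sex must drive the endpoints.** A sex difference in visceral fat area is a difference in level, whereas 9.1.3 defines the endpoints as changes from baseline. Subtracting baseline removes a stable difference in level. The documents give no sex effect on change.

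It is also fair to say that section 7.5 calls this an exploratory pilot study, where an unstratified list is a permissible choice. All of this stands, and it limits the point to precision and credibility. It does not remove the point: the method is undescribed, moderate imbalance is common at 40 patients, and 10.2 applies p < 0.05 to every test without adjustment.

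**Conclusion.** The point holds as a cheap improvement. As written, nothing in 6.2 limits imbalance by centre or sex, and nothing in 10.2 accounts for it. Under a 20:20 list, a gap of 4 or more men has probability 30% to 34% (12 or 20 men assumed). With two equal centres assumed, a 12:8 split or worse in a given centre has 34%, and 14:6 or worse about 3%. The consequence is lost precision and a less convincing result, not an invalid comparison. The sex figures do not depend on the number of centres. The centre figures do, and that number could not be checked. How much adjustment gains depends on how well the covariates predict change, which the documents do not say.

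**What to change.** **Section 6.2.** State how the list is made: generated separately for each centre, in permuted blocks of randomly varied size (for example 4 and 6), and concealed from those who enrol. Concealment matters because 13.1 has the investigator consult the list in an open-label trial, where small blocks of known size can be guessed. If a blocked or stratified list already exists, describe it.

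**Section 10.2.** Replace the unadjusted between-arm test of change with a linear model (ANCOVA) containing arm, the baseline value of the outcome, centre and sex, fitted at month 2 and at month 6. The section has no model now, so this replaces the test. Fix in advance a rule for pooling very small centres.

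Sex is handled by adjustment rather than as a stratum, because many strata are unworkable at 40 patients. Sex imbalance can therefore still arise, but the model accounts for it.

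**Cost.** Sample size and visits do not change. Section 9.2.1 already collects sex and the baseline values, and each patient's centre is known. The model uses a few degrees of freedom, which is a small net loss of precision if the covariates explain little of the variance in change. The overall split may be 19:21 rather than exactly 20:20.
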